# **APPENDICES**

## **APPENDIX A.**

#### i Adverse Events

In the situation where worsening in severity (including seriousness) occurs for an adverse event, study sites are instructed to enter an end date and start a new record for the adverse event. In the new record, the changed severity is to be recorded and the start date will be set to be the end date of the previous record. Data linking those records are collected in the data base. Consider three scenarios:

- The first AE record occurs prior to the first dose, the second AE record occurs on or after the first dose, and the severity increases: Only the second record will be counted as treatment emergent.
- Both records occur on or after the first dose: If the AE severity on the second record is worse than the severity on the first record, then count both records as treatment emergent.
- Both records occur on or after the first dose: If the AE one is severe and the other serious then count both records as treatment emergent.

Of note, when counting the total number of treatment-emergent events, events linked through change in severity will still be counted as separate events.

For events with missing start or stop dates, the following criteria will be used for the purpose of identifying treatment-emergent adverse events:

If both the start and stop date for a particular event are missing, then the event is considered to have occurred on or after the first dose of study treatment.

If the start date for a particular event is missing and the stop date/time falls after the first dose date/time, then the event is considered to have occurred on or after the first dose of study treatment.

If the start time is missing and the start date is same as the first dosing date, then the event is considered to have occurred on or after the first dose of study treatment.

If it cannot be determined whether or not an event has occurred on or after dosing due to a missing or partial date, then the event will be assumed to have occurred on or after the first dose for the purpose of identifying treatment-emergent adverse events.

Product: Nusinersen	Statistical Analysis Plan
Study: 232SM203	Version: 3.0 Final

Specifically, let AESTDT denote the start date of an adverse event and TRTSTDT be the start date of study treatment. For the purpose of identifying the treatment emergent adverse events, the following algorithm will be used for the imputation of missing or partial date:

If AESTDT is completely missing or the year is missing, then impute AESTDT to TRTSTDT.

If, in AESTDT, year is present and month/day are missing and year is equal to the year portion of TRTSTDT, then impute the month/day portion of AESTDT to the month/day portion of TRTSTDT.

If, in AESTDT, year is present and month/day are missing and year is not equal to the year portion of TRTSTDT, then impute the month/day portion of AESTDT to January 01.

Consider the situation in AESTDT where year and month are present with only day missing. If the year and month are the same as those for TRTSTDT, then impute day in AESTDT with day in TRTSTDT. Otherwise, impute the day in AESTDT with the first day of the month.

It is important to emphasize that the imputed date will not be used for calculations such as onset and duration of an adverse event.

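### The AE start-date imputation has no stop-date condition and conflicts with the criteria just above it, so an event known to have ended before first dose can be flagged treatment emergent

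*SAP*

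**What the plan says.** The rules are in Appendix A, i Adverse Events, of the Part B infantile-onset SAP. They recur in Appendix A, ii Adverse Events, of the Part B later-onset and Part C SAPs, and in Section 5.1 (Adverse Events) of the Part A SAP.

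Two sets of rules follow one another.

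- **Criteria.** An event counts as on or after dosing if both dates are missing, or under this condition: "If the start date for a particular event is missing and the stop date/time falls after the first dose date/time". There is also a fallback that assumes a record falls on or after first dose. It is limited to undeterminable timing and opens: "If it cannot be determined whether or not an event has occurred on or after dosing due to a missing or partial date, then the".
- **Algorithm.** In the Part B and Part C SAPs it is introduced thus: "For the purpose of identifying the treatment emergent adverse events, the following algorithm will be used for the imputation of missing or partial date". Its branches are:
  - start date or year missing: "If AESTDT is completely missing or the year is missing, then impute AESTDT to TRTSTDT";
  - year only, same year as first dose: "year is equal to the year portion of TRTSTDT, then impute the month/day portion of AESTDT to the month/day portion of TRTSTDT";
  - year only, different year: "year is not equal to the year portion of TRTSTDT, then impute the month/day portion of AESTDT to January 01";
  - day missing: the first-dose day if year and month match, and if not, "Otherwise, impute the day in AESTDT with the first day of the month".

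The definition of treatment emergence (Part A Section 5.7, Part B infantile-onset Section 7.1.1, Part B later-onset Section 6, Part C Section 5.7.1) requires that the event either was present before first dose and then worsened, or was absent before first dose and then appeared.

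**The concern.** The algorithm is the part a programmer would code, and none of its branches tests the stop date. An event from screening that resolved before dosing, but whose start was recorded incompletely, can therefore be moved to the day of first dose and attributed to the study treatment period.

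The SAPs expect pre-dose AE records: their worked scenarios include one that begins before first dose. AE incidence is a primary endpoint in Parts A and C, and the groups are small. If a participant enters an incidence row only because of such a record, that row moves by 1/6 = 16.7 percentage points in Part A (6 participants), 1/40 = 2.5 points in Part C (40 participants) and 1/25 = 4 points in the Part B infantile-onset control group (planned maximum 25).

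**Working it through.** The plan gives no figure to reproduce. The check compares the two rules on the same records.

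**One record.** First dose 15 March; AE start recorded as March with the day missing; stop 10 March.

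- Algorithm: year and month match first dose, so the start becomes 15 March. The event is treatment emergent and starts five days after it ended.
- Criteria: the start is only partly missing, the stop is before dosing, and the timing is determinable. No criterion places the event on or after dosing.
- Definition: the event did not worsen after first dose and did not newly appear after it. It is not treatment emergent.

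**Enumeration.** Inputs:

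- A 21-day screening period, from the study-period sections of the Part B and Part C SAPs. Part A gives its study periods as not applicable, so 21 days is an assumption there.
- Three first-dose dates, assumed for illustration: 15 June, 3 June and 10 January.
- Every whole-day start/stop pair lying 1 to 21 days before first dose, with stop on or after start: 21 × 22 / 2 = 231 pairs. All had ended before dosing.

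Where only matching dates move to first dose, the number flagged is n(n + 1)/2. Here n is the number of screening days in the same month (day missing) or the same year (month and day missing) as first dose.

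| Start date recorded | 15 June | 3 June | 10 January |
|---|---|---|---|
| Fully missing | 231/231 (100%) | 231/231 (100%) | 231/231 (100%) |
| Year only | n = 21: 231/231 (100%) | n = 21: 231/231 (100%) | n = 9: 45/231 (19%) |
| Year and month | n = 14: 105/231 (45%) | n = 2: 3/231 (1%) | n = 9: 45/231 (19%) |
| Complete | 0/231 | 0/231 | 0/231 |

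In every flagged case the imputed start is later than the event's own stop. With the stop date known, the criteria place none of the 231 on or after dosing. If a known pre-dose stop overrides the imputation, the count is 0/231 in every row.

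**The case against.** The strongest reply is that the algorithm is only the working-out of the fallback. In the Part B and Part C SAPs it directly follows the rule for undeterminable timing and is introduced as a specification of what precedes it. On that reading, a record with a known pre-dose stop never reaches it, and nothing is misclassified. This is a reasonable reading and it stands as a possibility. It is not stated, though: the introduction gives the scope as missing or partial dates generally. In Part A the introduction is absent and the two sets of rules sit in one bullet list with equal standing.

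Other points on that side are sound:

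- Partial dates move to first dose only when the year, or year and month, match; otherwise they go to 1 January or the first of the month.
- The error adds events, which is the cautious direction for safety.
- The same rule applies to both randomised arms.
- No efficacy test is affected.
- AEs are also listed individually in Parts B and C.

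Two replies carry less weight. Imputed dates are indeed not used for onset or duration, but the treatment-emergent flag is the algorithm's stated purpose. The statement that all events reported during the study are included, because of the long half-life, does not displace the definition; Part C says explicitly that inclusion follows the definition.

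**Conclusion.** The point holds as an unresolved conflict between two written rules, in all four SAPs. For an AE with a missing start (or a partial one matching first dose) and a known pre-dose stop, the algorithm taken literally gives a wrong classification, and no precedence is stated.

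A reader might infer that the plan has settled on counting pre-dose events as treatment emergent, or that every incomplete start date goes to first dose. The documents support neither: the criteria and the definition point the other way, and non-matching partial dates are placed elsewhere. A reader might also want one misclassification rate. None can be given: the illustration rests on assumed dosing dates and equal weight for every start/stop pair, and its shares apply only to records with both an incomplete start and a known pre-dose stop. The documents give no count of such records; it is probably small.

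This is a minor clarification worth making, because it costs almost nothing and AE incidence is a primary endpoint in two parts of the study.

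**What to change.** Add to the algorithm in each of the four SAPs:

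*If the stop date, or its known year or year/month part, is before first dose, the event is not treatment emergent and its start date is not imputed to TRTSTDT. The imputation applies only when timing relative to first dose cannot be determined.*

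This brings the AE rule into line with the concomitant-therapy rules in the same SAPs, which already compare the end date, complete or partial, with the first-dose date. The cautious fallback for undeterminable events stays as it is.

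The cost is one sentence per SAP and one condition in the derivation of the treatment-emergent flag. No new data are needed.

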#### ii Concomitant Therapy and Procedure

In order to define concomitant therapies with missing start or stop dates, the following additional criteria will be used:

- If both the start and stop dates of a particular therapy were missing, that therapy is considered concomitant.
- If the start date of a therapy was missing and the stop date of that therapy fell on or after the date of dosing, that therapy is considered concomitant.
- If the start date of a therapy was prior to the date of dosing and the stop date of that therapy was missing and the therapy was listed as continuing, that therapy is considered concomitant.
- If the start date of a therapy was prior to the date of dosing and the stop date of that therapy was missing and the therapy was listed as *not* continuing, that therapy is considered concomitant.
- If the start/stop date of a therapy is partial then where it is not possible to rule out that it was not taken concomitantly it will be considered concomitant.

Denote the end date of medications as CMENDT and the study treatment start date as TRTSTDT. The medication is classified concomitant provided any of the following is NOT true:

- CMENDT is complete and CMENDT is less than TRTSTDT.
- Day of CMENDT missing and year/month of CMENDT is strictly before year-month of TRTSTDT.

• Month of CMENDT is missing and year of CMENDT is strictly before year of TRTSTDT.

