### 7.1.2. Concomitant therapy and Procedure

A concomitant therapy is any drug or substance administered between screening and the final study visit/telephone call. Participants are instructed to contact their Investigators before taking any new medications, including nonprescription drugs and herbal preparations.

Throughout the study, Investigators or designated licensed physicians involved in the study may prescribe concomitant therapies (procedures) or treatments deemed necessary for AEs or to provide adequate supportive care.

Participants are prohibited from receiving other experimental or approved agents for the

treatment of SMA, including gene therapy, biological agent, or device, during the study. This includes marketed agents at experimental doses that are being tested for the treatment of SMA (oral albuterol/salbutamol, riluzole, carnitine, sodium phenylbutyrate, valproate, hydroxyurea, etc.).

All concomitant therapies will be coded using the World Health Organization drug

dictionary (WHO Drug). A concomitant procedure is any therapeutic intervention (e.g., surgery/biopsy, physical therapy) or diagnostic assessment (e.g., blood gas measurement, bacterial cultures) performed between Screening and the final study visit/telephone call. Concomitant procedures will be coded using MedDRA.

For the purposes of analysis, a concomitant therapy (including medication or procedure) is defined as any therapy that was taken or administered on or after the first injection of nusinersen (see appendix A). This includes therapies and procedures that were started prior to the initiation of injection of nusinersen if their use continued on or after the first injection of nusinersen. The number and percentage of subjects who were taking each type of concomitant therapy and procedures at baseline and during the study will be presented by preferred term.

The number and percentage of subjects who underwent each type of concomitant procedure during the study will be presented.

Concomitant therapies related to LP/Sham procedure will be summarized separately.

If there are a sufficient number of tests or treatments reported with indication of COVID-19, a separate summary of these will be provided.

Concomitant medications will also be reviewed by a medical reviewer prior to the lock to determine disallowed medications according to the protocol. These will be summarized separately.

Product: Nusinersen	Statistical Analysis Plan
Study: 232SM203	Version: 3.0 Final

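### The end-date rule for concomitant medication in all four SAPs is always satisfied, so it cannot exclude a medication that ended before the first dose

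*SAP*

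**What the plan says.** The body of each SAP defines concomitant therapy for analysis. In section 7.1.2 of the Part B infantile-onset SAP it is "any therapy that was taken or administered on or after the first injection of nusinersen", together with therapy started earlier and still in use on or after that injection. Section 5.5 of the Part A SAP, section 6.1.1 of the Part B later-onset SAP and section 5.5 of the Part C SAP say the same; Part C specifies the first injection received in the study. The two Part B SAPs and the Part C SAP send the reader to Appendix A at this point.

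The operational rule is in Appendix A of those three SAPs (item ii for Part B infantile-onset, item iii for the other two) and in section 5.1 of the Part A SAP. It reads: "The medication is classified concomitant provided any of the following is NOT true". The conditions are:

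1. "CMENDT is complete and CMENDT is less than TRTSTDT"
2. "Day of CMENDT missing and year/month of CMENDT is strictly before year-month of TRTSTDT"
3. "Month of CMENDT is missing and year of CMENDT is strictly before year of TRTSTDT"

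The lead-in and conditions are the same in all four SAPs, except that Part A abbreviates the treatment start date as TRTSDT. A bullet just above the rule deals with partial start or stop dates. It treats a therapy as concomitant where one cannot rule out that it was *not* taken concomitantly.

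**The concern.** Each condition is a way of showing that a medication stopped before treatment began. A medication should therefore count as concomitant only when none of them holds. The text asks instead that at least one of them fail, which is a much weaker requirement. If it is always met, the rule does no work, and a medication with a fully recorded end date before the first dose is still classified as concomitant. A derivation programmed to the letter would then put therapy that ended before treatment into tables meant to show therapy during treatment. Because the same wording stands in all four SAPs, no correct version of the rule exists for a programmer to follow.

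**Working it through.** The plan gives no figure to reproduce; this is a check of logic.

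**Inputs.** Conditions C1, C2 and C3 as quoted above, from Appendix A of the Part B infantile-onset SAP.

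**The two rules.**
- As written: concomitant if NOT C1, or NOT C2, or NOT C3. This equals NOT (C1 and C2 and C3).
- As the body definition requires: concomitant if NOT C1 and NOT C2 and NOT C3. This equals NOT (C1 or C2 or C3).

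**Can all three conditions be true together?** C1 requires a complete end date. C2 requires the day to be missing and C3 requires the month to be missing. C1 therefore excludes both C2 and C3, the conjunction is never true, and the rule as written is always satisfied.

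C2 and C3 need not exclude each other. When only the year is known and it is earlier than the first-dose year, both day and month are missing, and both conditions may be read as true. The result is unchanged, because C1 is then false.

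**Enumeration.** Take an example first-dose date of 15 June 2021. Let the end year be missing, 2020, 2021 or 2022; the month missing, May, June or July; and the day missing, 10, 15 or 20. That gives 4 × 4 × 4 = 64 patterns.

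Patterns known to end before the first dose:
- Complete dates: 3 × 3 = 9 in 2020, 3 in May 2021 and 1 on 10 June 2021, so 13.
- Day missing, month known: 3 in 2020 and 1 in May 2021, so 4.
- Month missing, year 2020: 4, one for each day value including missing.
- Total: 13 + 4 + 4 = 21.

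| Rule | Concomitant, of 64 | Concomitant among the 21 known to end earlier |
|---|---|---|
| As written (any condition untrue) | 64 | 21 |
| None of the conditions true | 64 − 21 = 43 | 0 |

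At most one condition is true at a time if a year-only date is kept out of C2, and at most two if it is counted there. The table is the same either way.

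**The partial-date bullet.** Where a partial date leaves the timing open, the literal and the intended readings both give concomitant. They part only where the partial date already settles the matter. For a therapy known to have ended earlier, one cannot rule out that it was not taken concomitantly, so the literal text includes it. The extra negative thus errs in the same direction as the main rule.

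**The case against.** The strongest reply is that this is a drafting slip with an obvious intent. The body definition is correct in every SAP, and the flawed sentence sits in a passage introduced as handling missing start or stop dates. The three conditions would be pointless under the literal reading, so a programmer may well code what was meant. That is fair as to intent. It does not rescue the rule: the first condition concerns complete dates, so the fault is not confined to missing ones, and three of the four SAPs point from the definition to this text.

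Three stronger readings are tempting, and the documents do not support them.

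- *All pre-study therapy would be counted.* The same body sections first limit a concomitant therapy to one given between screening and the final visit or call. Screening is 21 days in the Part B and Part C SAPs. How many therapies that ended before the first dose are recorded at all depends on data collection that the SAP does not describe. The rule misclassifies every such record, but their number is unknown and may be small.
- *Per-protocol exclusions would be wrong.* The Per Protocol Set definitions in the Part B and Part C SAPs concern SMA agents taken during the study and are settled as significant deviations before database lock. None refers to this end-date rule. The Part A SAP defines no Per Protocol Set.
- *The disallowed-medication summaries would be wrong.* In Parts B and C a medical reviewer decides these against the protocol and is not bound by the classification. The list put to the reviewer could be longer than it should be, which is as far as the text goes. Part A plans no such summary.

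**Conclusion.** The point holds as an error in an operational derivation rule. Followed literally, the rule classifies every recorded medication that ended before the first dose as concomitant, in all four SAPs, against their own definition. The logic needs no assumption beyond the text; the example dates only illustrate it.

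The direct effect is on the descriptive summaries of concomitant medications, and of procedures if the same rule is applied to them under the joint heading. Inflation of the list reviewed for disallowed medications in Parts B and C is possible but not shown. No per-protocol exclusion, efficacy endpoint, power or alpha is shown to be affected. The number of records involved cannot be derived from the documents. The rule should be corrected because it gives a wrong classification when followed, and correcting it is cheap.

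**What to change.** Make two wording changes in each SAP: section 5.1 of Part A, Appendix A item ii of Part B infantile-onset, and Appendix A item iii of Part B later-onset and of Part C.

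- Lead-in to the three conditions: state that a medication is concomitant provided *none* of them is true.
- Partial-date bullet: replace the double negative with *where it is not possible to rule out that it was taken on or after the first dose*.

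Then check that the derivation program excludes a complete end date before the first dose and a partial end date known to be earlier. The cost is two sentences in each of four documents and one program check.

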# **APPENDIX B.**

#### PERMANENT VENTILATION DEFINITION CRITERIA: ACUTE REVERSIBLE EVENT

Purpose: Acute, intercurrent events may result in transient utilization of increased respiratory support for participants with spinal muscular atrophy (SMA) in this study. Such events may not reflect irreversible SMA disease progression and may complicate the ability to detect the effects of nusinersen on SMA disease progression.

A secondary endpoint is defined as the time to death or permanent ventilation (tracheostomy or  $\geq$  16 hours of ventilation/day continuously for > 21 days in the absence of an acute reversible event).

The purpose of this appendix is to define an acute reversible event and to indicate how this prespecified definition will be used in this study.

Any one of the following that occur between 7 days before and 7 days after the onset of threshold-level respiratory support ( $\geq 16$  hours/day) meet the definition of an acute reversible event:

- 1. Fever  $\geq 102^{\circ}$ F/38.9°C (tympanic, rectal, axillary, skin, sublingual)
- 2. Infection

Blood, sputum, throat, or cerebrospinal fluid (CSF) culture positive  $\times$  2 for virus, bacteria, or fungus

Blood, throat, sputum, or CSF viral polymerase chain reaction positive

Blood, throat, sputum, or CSF for infectious antigen diagnostic (e.g., streptococcus+ or hepatitis B surface antigen positive)

Blood, throat, sputum, or CSF positive for direct microscopic visualization (e.g., bronchoalveolar lavage or Gram stain revealing the presence of bacteria by tissue biopsy

